2. ABBREVIATIONS

Abbreviations pertain to the Statistical Analysis Plan (SAP) only (not the tables, figures and listings [TFLs]).

| | |
|------------------|---|
| AE | Adverse event |
| ALP | Alkaline phosphatase |
| ALT | Alanine aminotransferase |
| AST | Aspartate aminotransferase |
| AUC | Area under the concentration versus time curve |
| AUC(0-∞) | Area under the concentration versus time curve from zero to infinity |
| AUC(0-tlast) | Area under the concentration versus time curve from time zero to time t, where t is the last time point with a measurable concentration |
| %AUC(tlast-∞) | Percentage of AUC(0-∞) extrapolated |
| BMI | Body mass index |
| BQL | Below the level of quantitation |
| C _{max} | Maximum observed drug concentration |
| CI | Confidence interval |
| CL/F | Apparent total body clearance of drug calculated after extra-vascular administration |
| CRF | Case Report Form |
| CSR | Clinical Study Report |
| CRU | Clinical Research Unit |
| CV | Coefficient of variation |
| EC | Early Clinical |
| ECG | Electrocardiogram |
| e.g. | For example (Latin: exempli gratia) |
| GGT | Gamma-glutamyl transferase |
| ICH | International Council on Harmonisation |
| LLOQ | Lower limit of quantitation |
| MedDRA | Medical Dictionary for Regulatory Activities |
| MR | Metabolic ratio |
| MRE | Magnetic resonance elastography |

| | |
|------------|--|
| MW | Molecular weight |
| PK | Pharmacokinetic |
| SAP | Statistical Analysis Plan |
| SD | Standard deviation |
| TBL | Total bilirubin |
| TFLs | Tables, Figures, and Listings |
| $t_{1/2}$ | Half-life associated with the terminal rate constant (λ_z) in non-compartmental analysis |
| t_{\max} | Time of maximum observed drug concentration |
| ULN | Upper limit of normal |
| V_{ss}/F | Apparent volume of distribution during the terminal phase after extra-vascular administration |
| V_z/F | Apparent volume of distribution during the terminal phase after extra-vascular administration |
| WHO | World Health Organization |

3. INTRODUCTION

This SAP has been developed after review of the Clinical Study Protocol (final version dated 27 April 2017).

This SAP describes the planned analysis of the safety, tolerability and pharmacokinetic (PK) data from this study. A detailed description of the planned TFLs to be presented in the clinical study report (CSR) is provided in the accompanying TFL shell document.

The intent of this document is to provide guidance for the statistical and PK analyses of data. In general, the analyses are based on information from the protocol, unless they have been modified by agreement between Eli Lilly and Company and Covance Early Clinical (EC) Biometrics. A limited amount of information concerning this study (e.g., objectives, study design) is given to help the reader's interpretation. This SAP must be signed off prior to first subject administration for this study. When the SAP and TFL shells are agreed upon and finalized, they will serve as the template for this study's CSR.

This SAP supersedes the statistical considerations identified in the protocol; where considerations are substantially different, they will be so identified. If additional analyses are required to supplement the planned analyses described in this SAP, they may be performed and will be identified in the CSR. Any substantial deviations from this SAP will be agreed upon between Eli Lilly and Company and Covance EC Biometrics and identified in the CSR. Any minor deviations from the TFLs may not be documented in the CSR.

This SAP is written with consideration of the recommendations outlined in the International Council on Harmonisation (ICH) E9 Guideline entitled Guidance for Industry: Statistical Principles for Clinical Trials¹ and the ICH E3 Guideline entitled Guidance for Industry: Structure and Content of Clinical Study Reports².

4. STUDY OBJECTIVES

4.1 Primary objective

- To determine the PK of lasmiditan in healthy elderly subjects (≥ 65 years of age) following a single 200 mg oral dose of lasmiditan.

4.2 Secondary objectives

- To compare the PK of lasmiditan in healthy elderly subjects (≥ 65 years of age) against the PK of lasmiditan in healthy young subjects (18 to 45 years of age) following a single 200 mg oral dose of lasmiditan.
- To assess the safety and tolerability of a single 200 mg oral dose of lasmiditan in elderly and young healthy subjects.

4.3 Exploratory objective

- To determine the PK of the metabolites M8, M7, and M18 in healthy elderly and young subjects following a single 200 mg oral dose of lasmiditan.

5. STUDY DESIGN

This is a single dose study to determine the PK of lasmiditan following a single 200 mg oral dose in healthy elderly and young subjects. Two groups of subjects will be evaluated as follows:

- Group 1 (healthy elderly subjects; ≥ 65 years): 200 mg lasmiditan and placebo in a randomized, double-blind, 2-period crossover design.
- Group 2 (healthy young subjects; 18 to 45 years, inclusive): 200 mg lasmiditan in an open label design.

Subjects in Group 2 will be matched by primary race, sex, and body mass index (BMI) ($\pm 20\%$) to subjects in Group 1 where feasible. Both groups may be studied concurrently.

Screening Period:

All subjects will participate in a screening visit up to 28 days prior to study drug dosing.

Dosing Period:

Subjects in Group 1 will participate in 2 dosing periods. They will be admitted to the clinical research unit (CRU) on the day prior to dosing (Day -1), and receive study drug on Day 1 for each dosing period. Subjects may be discharged from the CRU on Day 3 based on investigator discretion. There will be a washout period of 3 to 10 days between each dose. Subjects may stay in the CRU as inpatient during the entire dosing period.

Subjects in Group 2 will participate in 1 dosing period. They will be admitted to the CRU on Day -1 and receive study drug on Day 1. Subjects may be discharged from the CRU on Day 3 based on investigator discretion.

All subjects will be discharged from the study approximately 7 days post their final dose of lasmiditan.

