9.4 Safety and Tolerability Assessments

9.4.1 Adverse events

Where changes in severity are recorded in the Case Report Form (CRF), each separate severity of the adverse event (AE) will be reported in the listings, only the most severe will be used in the summary tables. A pre-existing condition is defined as an AE that starts before the subject has provided written informed consent and is ongoing at consent. A non-treatment emergent AE is defined as an AE which starts after informed consent but prior to dosing. A treatment-emergent AE is defined as an AE which occurs postdose or which is present prior to dosing and becomes more severe postdose.

All AEs will be listed. Treatment-emergent AEs will be summarized by age group, treatment, severity and relationship to the study drug. The frequency (the number of adverse events, the number of subjects experiencing an adverse event and the percentage of subjects experiencing an adverse event) of treatment-emergent adverse events will be summarized by age group, treatment, Medical Dictionary for Regulatory Activities (MedDRA) version 20.0 system organ class and preferred term. The summary and frequency adverse event tables will be presented for all causalities and those considered related to the study drug. Any serious adverse events will be tabulated.

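### Does timing study discharge from the final lasmiditan dose undermine the elderly crossover and its adverse event summaries?

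*SAP*

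**What the plan says.** Section 5 of the SAP describes Group 1 as receiving "200 mg lasmiditan and placebo in a randomized, double-blind, 2-period crossover design". It adds that "Subjects in Group 1 will participate in 2 dosing periods", with admission the day before dosing and a dose on Day 1 of each. On spacing it says: "There will be a washout period of 3 to 10 days between each dose". On leaving the unit: "Subjects may be discharged from the CRU on Day 3 based on investigator discretion". Group 2 is simpler: "Subjects in Group 2 will participate in 1 dosing period", open label, lasmiditan only.

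The section closes with one rule for both groups: "All subjects will be discharged from the study approximately 7 days post their final dose of lasmiditan". Nothing elsewhere in the SAP makes an exception for elderly subjects who take lasmiditan first, or sets a discharge time from the placebo dose.

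The placebo-period data are used in Section 9.4.1, where "Treatment-emergent AEs will be summarized by age group, treatment, severity and relationship to the study drug". Section 9.4.5 does the same for vital signs, with a separate predose baseline in each treatment period. Section 9.4.8 plans no inferential safety analysis.

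**The concern.** In the lasmiditan-then-placebo sequence, the only lasmiditan dose, and therefore the final one, is given in Period 1. A clock started at that dose may run out soon after the placebo dose, on the same day, or before it. The rule would then collide with the requirement that Group 1 completes two periods.

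Two consequences would matter if the rule were applied as written. First, post-placebo observation would be cut short in one sequence only. Elderly placebo is the only control in the study, so fewer placebo events might be recorded and the descriptive contrast with lasmiditan would look worse for the drug. Second, the discharge date would depend on sequence, so that applying the rule would need, or would reveal, the treatment order in a double-blind group.

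**Working it through.** **Inputs, all from SAP Section 5.** Discharge about 7 days after the final lasmiditan dose; interval between doses w = 3 to 10 days; two periods in Group 1; earliest release from the unit on Day 3, which is 2 days after a dose. The plan states no figure of its own to reproduce.

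**Step 1: literal reading, lasmiditan first.** Count days from the lasmiditan dose. Placebo falls on day w, Period 2 Day 3 on day w + 2, and discharge on day 7. Discharge minus placebo is therefore 7 − w.

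| w (days) | Discharge relative to placebo, 7 − w | Period 2 Day 3, days after lasmiditan, w + 2 |
|---|---|---|
| 3 | +4 | 5 |
| 4 | +3 | 6 |
| 5 | +2 | 7 |
| 6 | +1 | 8 |
| 7 | 0 | 9 |
| 8 | −1 | 10 |
| 9 | −2 | 11 |
| 10 | −3 | 12 |

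At w = 8 to 10 discharge precedes the second dose. At w = 6 to 10 it precedes Period 2 Day 3. The word approximately may absorb a day, but not this range. Placebo-first subjects and Group 2 have no conflict, because their lasmiditan dose is their last dose.

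**Step 2: what literal use would do to observation time.** Assume equal allocation to sequences and assign each event to the most recent dose. For w up to 7:

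- Lasmiditan is observed for w days in lasmiditan-first subjects and 7 days in placebo-first subjects, a mean of (w + 7)/2.
- Placebo is observed for 7 − w days and w days respectively, a mean of 7/2 = 3.5.

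At w = 3 this gives 5 days against 3.5; at w = 7 it gives 7 against 3.5.

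**Step 3: the same sum if the sentence is loose wording for the last study dose.** Each treatment is then observed for w days when given first and 7 days when given second. The mean is (w + 7)/2 for both: 5 and 5 at w = 3, 7 and 7 at w = 7, 8.5 and 8.5 at w = 10. The imbalance comes entirely from the literal reading.

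**Step 4: which reading the document supports.**

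- Section 5 itself has every Group 1 subject admitted and dosed in both periods, which rules out discharge before the second dose.
- Section 9.4.5 takes a baseline in each treatment period, so the analysis sections expect data from both.
- Group 1 is double-blind, so staff who do not know the sequence cannot count days from lasmiditan.
- Section 3 says that design information is included as an aid to interpretation, and that the SAP replaces the protocol's statistical considerations. It does not claim to replace the visit schedule.

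**Step 5: what depends on the sentence.** The age comparison in Section 9.3.2 uses lasmiditan and metabolite data and contains no placebo term. The precision statement in Section 7 rests on 15 subjects per group and a 40% CV. The tables in Sections 9.4.1 and 9.4.5 are by age group and treatment under either reading.

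**The case for a change.** The best case for a change is that the SAP's own vocabulary does not settle the matter. Section 5 uses study drug for the dose in each period, so a term covering both doses was available and was not used for discharge. Section 8 then names placebo separately from study drug. Section 3 says the SAP and table shells will form the template for the study report, so the wording could be carried forward. Section 9.4.1 calls an event treatment-emergent if it occurs after dosing, with no window and no rule tying an event to a period. Safety is a secondary objective, and rewording costs little.

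What stands is that the sentence is inaccurate for one sequence and nothing in the SAP corrects it. The discharge sentence and the two-period description do have to be reconciled with each other and with the protocol's schedule, which is not at hand. Which schedule is right is not for this review to say.

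The rest does not carry the point further. Bias and unblinding both need someone to schedule visits from the SAP's background text while knowing the sequence. A sentence repeated in the report would be a description, not a result. The missing event window is a separate matter: it would be the same question if the discharge sentence were flawless. Analysts would ordinarily assign an event to the most recent dose, and the summaries are descriptive only. The safety objective in Section 4.2 concerns lasmiditan in elderly and young subjects and states no formal comparison with placebo.

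**Conclusion.** The observation about the text is correct and the arithmetic holds: +4 to −3 days from placebo to discharge in the lasmiditan-first sequence, affecting 7 or 8 of 15 elderly subjects if sequences are equally allocated. It is nevertheless a clerical slip in a descriptive section. Rewording it would alter no estimate, interval, table or conclusion, so no change to the analysis plan follows.

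This rests on two assumptions: that visits are run from the protocol rather than from SAP Section 5, and that the protocol's schedule covers both Group 1 periods without reference to treatment. If the protocol carried the same sentence as an operating instruction, the literal consequences in Steps 1 and 2 would need a fresh look, but the SAP alone gives no ground for supposing that sites act on it.

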6. TREATMENT

The following is a list of the study treatments and age group names that will be used in the TFLs.

| Treatment Name | Order in TFL |
|-------------------|--------------|
| Placebo | 1 |
| 200 mg lasmiditan | 2 |

| Age Group Name | Order in TFL |
|----------------|--------------|
| Elderly | 1 |
| Young | 2 |

7. SAMPLE SIZE JUSTIFICATION

Up to 36 subjects may be enrolled in order that 30 subjects (2 groups of 15) complete the study. For area under the curve (AUC) or maximum observed drug concentration (C_{max}), assuming inter-subject coefficient of variation (CV) of 40% and a sample size of 15 per group, the 90% confidence interval around the ratio of the geometric means (elderly group : non-elderly group) will have half-width of 24.3% on the log scale with 90% coverage probability.

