9. STATISTICAL METHODOLOGY

9.1 General

Data listings will be provided for all data that is databased. Summary statistics and statistical analysis will only be presented for data where detailed in this SAP. For continuous data, summary statistics will include the arithmetic mean, arithmetic standard deviation (SD), median, min, max and N; for log-normal data (e.g. the PK parameters: AUCs and C_{max}) the geometric mean and geometric CV% will also be presented. For categorical data, frequency count and percentages will be presented. Data listings will be provided for all subjects up to the point of withdrawal, with any subjects excluded from the relevant population highlighted. Summary statistics and statistical analyses will generally only be performed for subjects included in the relevant analysis population. For the calculation of summary statistics and statistical analysis, unrounded data will be used.

Mean change from baseline is the mean of all individual subjects’ change from baseline values. Each individual change from baseline will be calculated by subtracting the individual subject’s baseline value from the value at the timepoint. The individual subject’s change from baseline values will be used to calculate the mean change from baseline using a SAS procedure such as Proc Univariate.

Data analysis will be performed using SAS[®] Version 9.3 or greater.

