9.3.2 Pharmacokinetic Statistical Methodology

The PK parameter estimates will be evaluated to determine the impact of age on the PK of lasmiditan and its metabolites. Log-transformed C_{\max} and $AUC(0-\infty)$ will be evaluated in a linear fixed-effects model with a fixed effect of age group (elderly, young). The 90% confidence intervals (CIs) of the ratios of geometric means of the elderly group versus the young group will be presented. An example of the SAS code that will be used is as follows:

```
proc mixed data=xxx;  
class agegroup;  
model l_pk = agegroup / alpha=0.1;  
lsmeans agegroup / pdiff;  
run;
```

where l_pk is the log-transformed (base e) PK parameter.

The t_{\max} will be analyzed using a Wilcoxon rank sum test. Estimates of the median difference between elderly and young subjects based on the observed medians, 90% CIs and the p-value from the Wilcoxon test will be calculated.

Additional analysis will be performed if warranted upon review of the data.

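### SAP Section 7 gives 24.3% as a log-scale half-width, but CV 40% with 15 per group gives 0.278; 24.3% is only the lower arm of the back-transformed interval

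*SAP*

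**What the plan says.** Section 7 justifies the sample size by precision. The enrolment aim is "Up to 36 subjects may be enrolled in order that 30 subjects (2 groups of 15) complete the study". For AUC or Cmax, "assuming inter-subject coefficient of variation (CV) of 40% and a sample size of 15 per group", it states that "the 90% confidence interval around the ratio of the geometric means" (elderly : non-elderly) "will have half-width of 24.3% on the log scale with 90% coverage probability". It gives no formula and does not say how the CV was converted to a log-scale SD.

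The other inputs are in Section 9. Section 9.1 treats these parameters as log-normal: "for log-normal data (e.g. the PK parameters: AUCs and C_{max}) the geometric mean and geometric CV% will also be presented". Section 9.3.2 fits a model with age group as the only effect, so the two groups are independent, and says that "l_pk is the log-transformed (base e) PK parameter". The 90% intervals "of the ratios of geometric means of the elderly group versus the young group will be presented".

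**The concern.** A half-width on the log scale is symmetric about the log ratio and becomes an asymmetric interval once exponentiated. A percentage labelled as log-scale therefore has to be the log-scale quantity itself, 0.243. If it is instead one arm of the back-transformed interval, the label is wrong and the wider arm goes unreported.

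This sentence is the SAP's only justification for 15 per group, and the ratio with its 90% interval is the main inferential result on Cmax and AUC. A reader who exponentiates ±0.243 will expect tighter limits than the design supports. The larger shortfall is on the upper side, which is the side that shows higher exposure in the elderly. Section 3 makes the SAP a template for the study report, so the sentence could be carried forward.

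**Working it through.** **Inputs**

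- CV 40%, 15 per group, two-sided 90% interval, 90% probability attached to the half-width: Section 7.
- Log-normal parameters: Section 9.1.
- Natural log, age group as the only effect, hence 15 + 15 − 2 = 28 degrees of freedom: Section 9.3.2.

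**Step 1. Log-scale half-width**

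- SD: σ = √ln(1 + 0.40²) = √ln(1.16) = 0.3853
- Standard error of the difference: 0.3853 × √(2/15) = 0.1407
- Half-width at the planning SD: t(0.95, 28) × SE = 1.7011 × 0.1407 = 0.2393
- Allowance for the estimated SD at 90% probability: √(χ²(0.90, 28)/28) = √(37.916/28) = 1.1637
- Half-width not exceeded with 90% probability: w = 0.2393 × 1.1637 = **0.2785**

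**Step 2. Reproducing the plan's figure**

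- Lower arm: 1 − exp(−0.2785) = 0.2431, i.e. **24.3%**
- Upper arm: exp(0.2785) − 1 = 0.3211, i.e. **32.1%**

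With every stated input used as written, 24.3% appears as the lower arm on the ratio scale and not as the log-scale half-width.

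**Step 3. The printed sentence taken literally**

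| | Log half-width | Lower limit ÷ estimate | Upper limit ÷ estimate |
|---|---|---|---|
| As printed | 0.243 | exp(−0.243) = 0.784 (−21.6%) | exp(0.243) = 1.275 (+27.5%) |
| From the stated inputs, 90% probability | 0.2785 | 0.757 (−24.3%) | 1.321 (+32.1%) |

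- P(half-width ≤ 0.243) = P(χ²₂₈ ≤ 28 × (0.243/0.2393)²) = 0.581, not 0.90.
- A log half-width of 0.243 with 90% probability needs about 19 per group: w = 0.2495 at 18 and 0.2417 at 19.

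**Step 4. How specific the match is**

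| Change from the stated inputs | Log half-width | Lower arm |
|---|---|---|
| None | 0.2785 | 24.3% |
| 14 per group | 0.2905 | 25.2% |
| 16 per group | 0.2678 | 23.5% |
| 89% probability | 0.2766 | 24.2% |
| 91% probability | 0.2805 | 24.5% |
| CV 39% | 0.2720 | 23.8% |
| CV 41% | 0.2849 | 24.8% |
| SD taken as 0.40 | 0.2891 | 25.1% |
| Conditional on the interval covering the true ratio (simulation) | 0.2798 | 24.4% |

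**Step 5. Other routes to 24.3%**

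Two routes that keep the 90% interval and the 90% probability give the figure on the log scale, but each departs from something in the SAP:

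- SD = ln(1 + CV) = ln(1.40) = 0.3365 gives w = 0.2432. For log-normal data that SD corresponds to a CV of about 34.6%, not 40%.
- 18 per group with a normal quantile in place of t gives w = 0.2427. Section 7 states 15 per group.

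A third keeps 15 per group but drops the 90% probability and leaves the log scale: with SD 0.40 and a normal quantile, half the width of the back-transformed interval is 0.2426.

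**The case against.** The strongest objection is to the diagnosis. The SAP does not show its calculation, and the conversion SD = ln(1 + CV) yields 0.2432 on the log scale, exactly as labelled. On that route the label is right and the SD is wrong. This stands as a limit on what can be said about the cause. It does not save the sentence, because that SD is not the one implied by a CV of 40%, and the log-scale figure for the stated inputs remains 0.278.

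The second objection is that little depends on the figure. It is a descriptive precision statement. Section 9.3.2 sets no equivalence limit and calculates the interval from the observed data. The half-width at the planning SD, 0.239, is also close to 0.243, so someone who takes 24.3% as typical log-scale precision is not far out. This stands and keeps the severity low. But the sentence attaches a 90% probability, and that is what fails: about 58% in place of 90%.

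The third objection is that the phrase coverage probability is only terminology. That is largely right. Coverage usually means the chance that the interval contains the true ratio, whereas the 90% that reproduces the figure is the chance that the half-width is not exceeded. Readers can work this out, so it is a wording note and not a second error.

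**Conclusion.** The concern holds. For CV 40%, 15 per group and 90% probability, the log-scale half-width of the 90% interval is 0.278, which is 0.2785/0.243 = 1.15 times the printed value. The limits relative to the estimated ratio are 24.3% below and 32.1% above. Read literally, the printed sentence implies 21.6% below and 27.5% above, so it understates the upper arm by 4.6 percentage points and the lower by 2.7.

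This rests on log-normal parameters with σ = √ln(1 + CV²), equal variances, two independent groups of 15 with 28 degrees of freedom, and the second 90% being the probability that the half-width is not exceeded. That 24.3% is a mislabelled lower arm is the likely explanation and not a proven one. That it is wrong on the stated scale does not depend on the explanation.

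The sample size, the analysis model and the results are unaffected. It should be corrected, at low severity.

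**What to change.** Keep 15 per group and replace the precision sentence in Section 7 with wording such as:

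> With an inter-subject CV of 40% and 15 completers in each group, there is a 90% probability that the half-width of the 90% CI is no more than 0.278 on the natural-log scale. The limits then lie no more than 24.3% below and 32.1% above the estimated elderly : young ratio of geometric means.

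This also replaces the term coverage probability with plain probability. The sponsor should check its own calculation to confirm which route produced 24.3%; if the SD was taken as ln(1.40), the same replacement text applies. The cost is one sentence of SAP text, with no change to the sample size, analysis or outputs.
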